**Table 8: Schedule of Assessments (Parts A and B) – Blood and Immune Cell Composition**

Assessments	Day 1 (Parts A and B) and Repeated on Day 2 (Part B Only)						Apheresis Product a	
	Within 1 Hour Prior to Plerixafor Dosing	1 Hour After Plerixafor Dosing	Within 15 Min Prior to MGTA Dosing	Post MGTA-145 Dosing				
				30 Min Prior to Apheresis	15 Min Prior to Apheresis	5 Min Prior to Apheresis		
Peripheral Blood CD34 + analysis	X	X	X			X		
Graft Immunophenotyping							X a	
PK blood samples b			X	X	X	X b		
CFU analysis							X a	

a Samples will be aliquoted from final HPA-C

b PK time points are within 15 minutes prior to MGTA-145 dosing and at 2 time points, spaced at least 15 minutes apart, prior to the initiation of apheresis. If apheresis is not initiated within 45 minutes of MGTA-145 dosing, a third PK sample is to be drawn within 5 minutes prior initiation of apheresis.

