**Protocol Number:**

145-SCD-204

**Phase:** Phase 2

**Country:** United States (US)

[figure not shown]
**Title of Study:** A Phase 2, open-label study to evaluate the efficacy and safety of MGTA-145 in combination with plerixafor for the mobilization of hematopoietic stem cells in patients with sickle cell disease

**Study Center(s):** Approximately 3 US study centers are planned for enrollment of subjects.

**Number of Subjects:** Approximately 10 to 14 evaluable subjects are planned to be enrolled in this two-part study.

- **Part A** has a planned enrollment of approximately 7 to 11 evaluable subjects.
- **Part B** has a planned enrollment of approximately 3 evaluable subjects.

**Study Design:** This is a two-part Phase 2, open-label, multicenter study. The study design is illustrated below.

**Methodology:** Approximately 10 to 14 patients with sickle cell disease (SCD) are planned to be enrolled in this 2-part study. Part A evaluates single-day mobilization and apheresis in 2 sequential patient cohorts, then Part B evaluates two-day mobilization and apheresis in a single

patient cohort, following administration of 2 consecutive-day single doses of MGTA-145 and plerixafor, respectively.

**Part A and Data Monitoring Committee (DMC) assessment:** Part A has a planned enrollment of approximately 7 to 11 evaluable subjects. The first cohort of 4 subjects is to receive a single 0.24 mg/kg subcutaneous (SC) dose of plerixafor followed 2 hours later by a single 0.03 mg/kg intravenous (IV) dose of MGTA-145. Apheresis is planned to commence within approximately 30 minutes of MGTA-145 dosing. For this initial cohort, only one subject will be dosed and apheresed on a single-day, and each subject will complete the 1-week follow-up visit before a subsequent subject can be dosed.

After the first cohort has completed the 1-week follow-up visit, an independent DMC, comprising of 3 members with medical expertise in stem cell transplantation and treatment of patients with SCD, will evaluate the safety, pharmacokinetics (PK), and mobilization kinetics of MGTA-145 before the second cohort of subjects is allowed to be enrolled. The DMC may recommend enrolling an additional 3 subjects at the 0.03 mg/kg MGTA-145 dose, an additional 7 subjects at a reduced dose of 0.015 mg/kg MGTA-145, or an alternative but lower dosing regimen for this cohort. The MGTA-145 dose will not be escalated during either Parts A or B of the study.

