**Secondary Endpoints; Parts A & B:**

Peak peripheral blood CD34+ counts will be summarized by time point relative to MGTA-145 dosing. Apheresis collection yields after 2 consecutive days of mobilization will be summarized for Part B.

Plasma concentrations of MGTA-145 will be listed, and a summary by time point for each dose cohort will be presented. Graphs of the individual subject concentration versus time profiles, as well as the arithmetic mean ( $\pm$ SD) concentration versus nominal time profiles, will be presented on a linear and log (concentration)/linear (time) scale.

All exploratory endpoints will be analyzed using descriptive statistics as well as graphical methods, when appropriate.

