#### 10.2.2. Apheresis Yield

Apheresis cell collection as outlined in the Schedule of Events ([Table 6](#) for Part A and [Table 7](#) for Part B) from all subjects enrolled in Parts A and B will proceed according to standardized procedures and start within an hour after MGTA-145 infusion. All subjects will undergo apheresis collection according to institutional practice, not to exceed a total of 8 hours. Apheresis yield will be measured as the total nucleated cell count and CD34+ cell count in absolute numbers and per kilogram. These determinations will be performed using fluorescent flow cytometry.

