#### **12.4.3. Pharmacokinetics**

Plasma concentrations of MGTA-145 will be listed and a summary by time point for each dose cohort will be presented using descriptive statistics (n, mean, SD, median, and range).

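### Post-dose PK draws are timed backward from an apheresis start that the protocol states in three ways, so by-time-point summaries pool samples taken up to 30 minutes apart after dosing

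*Protocol*

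**What the plan says.** Under the heading "Post MGTA-145 Dosing", Table 8 marks PK samples in three columns, all counted back from apheresis. The first is labelled "30 Min Prior to Apheresis"; the others are 15 and 5 minutes before apheresis. Footnote b governs these cells: "PK time points are within 15 minutes prior to MGTA-145 dosing and at 2 time points, spaced at least 15 minutes apart, prior to the" start of apheresis. The 5-minute draw is conditional: "If apheresis is not initiated within 45 minutes of MGTA-145 dosing, a third PK sample is to be drawn within 5 minutes prior initiation of" the procedure. Section 10.1 repeats both rules. Apart from the pre-dose sample, only the 45-minute trigger for the third draw refers to MGTA-145 dosing.

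The apheresis start, which anchors the draws, is stated in three places:

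- Synopsis, Part A: "Apheresis is planned to commence within approximately 30 minutes of MGTA-145 dosing".
- Section 6.3: about 30 to 45 minutes after dosing.
- Section 10.2.2: "start within an hour after MGTA-145 infusion".

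The infusion lasts 3 to 10 minutes (Section 9.5). Neither the Synopsis nor Section 6.3 says whether dosing means its start or its end.

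For analysis, Section 12.4.3 says that "a summary by time point for each dose cohort will be presented using descriptive statistics". The Synopsis (Secondary Endpoints) adds a listing, individual concentration-time graphs, and "arithmetic mean ( $\pm$ SD) concentration versus nominal time profiles". PK exposure is a secondary endpoint in Part B (Table 5) and is listed as such for Part A in the Synopsis.

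**The concern.** A nominal PK time point is useful when it means roughly the same time since dosing in every subject. Here the label means the same time before a procedure whose start may differ between subjects and sites. One row of the summary table, or one point on the mean curve, can then combine samples from different parts of the concentration curve. The resulting spread would look like between-subject PK variability.

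The first label also sits awkwardly with the planned timing. If apheresis starts 30 minutes after dosing or sooner, a sample 30 minutes before it cannot be a post-dose sample, which is what its heading calls it.

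At stake is the descriptive PK output for a secondary endpoint, which also feeds the DMC reviews after each Part A cohort. The cohorts are small (4, then 3 or 7 in Part A, and 3 in Part B), so timing differences will not average out. A later analysis plan can choose how to use recorded times, but it cannot re-time blood that has already been drawn.

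**Working it through.** The protocol states no figure on this point that could be reproduced. The check is timing arithmetic.

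**Inputs.** Apheresis start S = 30, 45 or 60 minutes after dosing (Synopsis, Section 6.3, Section 10.2.2). Lead time b = 30, 15 or 5 minutes (Table 8). Infusion length 3 to 10 minutes (Section 9.5).

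**Step 1: post-dose time of each draw.** Time = S − b.

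| Apheresis start S | 30 min prior | 15 min prior | 5 min prior |
|---|---|---|---|
| 30 | 30 − 30 = 0 | 30 − 15 = 15 | not required |
| 45 | 45 − 30 = 15 | 45 − 15 = 30 | not required |
| 60 | 60 − 30 = 30 | 60 − 15 = 45 | 60 − 5 = 55 |

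The third draw is required only when apheresis has not started within 45 minutes. Its labelled time therefore runs from about 45 − 5 = 40 to 55 minutes.

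**Step 2: spread within a label.** Across starts of 30 to 60 minutes, each routine label covers 30 minutes (0 to 30, and 15 to 45). Across the Section 6.3 window of 30 to 45 minutes, each covers 15 minutes (0 to 15, and 15 to 30). The labels are 30 − 15 = 15 minutes apart. In the wider range, one subject's earlier-labelled sample (30 minutes post-dose, start at 60) can come later than another's later-labelled sample (15 minutes post-dose, start at 30). Within the Section 6.3 window the two labels just meet at 15 minutes.

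**Step 3: is the first draw post-dose?** With S = 30 it falls at 0. If dosing means the start of infusion, that is 3 to 10 minutes before the infusion ends; if it means the end, the draw is at the end of infusion. For an earlier start, which the Synopsis wording allows, it falls before dosing: for example, 20 − 30 = −10 minutes.

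**Step 4: effect on concentration (assumption).** The protocol gives no half-life. Assuming mono-exponential decline after the infusion, the ratio between two samples Δ minutes apart is 2^(Δ/t½).

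| Assumed t½ (min) | Δ = 15 | Δ = 30 |
|---|---|---|
| 15 | 2.0 | 4.0 |
| 30 | 1.41 | 2.0 |
| 60 | 1.19 | 1.41 |
| 120 | 1.09 | 1.19 |

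These ratios suit the 15-minute-prior column. They do not apply to a sample at the start of infusion, where decline has not begun.

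**The case against.** The strongest reply is that footnote b and Section 10.1 are looser than the column labels. They ask only for two draws at least 15 minutes apart before apheresis. With a 30-minute start, a site could draw at about 10 and 25 minutes, both post-dose and consistent with the footnote. This stands. A reader might infer that the first sample will not be post-dose at all; the documents do not support that as a certainty, because the heading shows the intent and the footnote leaves room to meet it. But such draws depart from the column labels, and they leave no common nominal time to summarize.

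Second, the nominal-time outputs are not the only PK outputs. Listings and individual profiles are also planned, Section 12.3 summarizes infusion time and duration, and the Laboratory Manual or SAP may provide for actual draw times. This also stands. It would be wrong to infer that the PK data as a whole are lost: with actual times, individual profiles and exposure estimates can be recovered. The summary by label cannot.

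Third, a reader might infer that timing differences could distort the DMC's first choice between 0.03 and 0.015 mg/kg. They cannot do so as a dose contrast, because all 4 subjects in the first cohort receive 0.03 mg/kg. A cross-dose comparison arises only at the second review, and only if a lower dose has been used. The DMC also weighs safety and mobilization, and the stopping rules in Section 6.6 do not use PK.

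Fourth, the hour in Section 10.2.2 is an outer limit, and the Section 6.3 window halves the spread. That is correct, and both figures are given here.

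**Conclusion.** The point holds for the nominal-time summaries. As scheduled, the routine post-dose PK draws have no fixed relation to the MGTA-145 infusion. The by-time-point tables and mean profiles would pool samples up to 30 minutes apart in post-dose time, or 15 minutes apart if apheresis always starts within the Section 6.3 window. For a start at or under 30 minutes, the first column label contradicts its own heading.

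The timing result rests only on the protocol's stated times. The concentration effect does not: a 30-minute difference could mean anything from 1.19-fold to 4-fold over assumed half-lives of 120 down to 15 minutes. A reader might conclude that timing noise exceeds the 2-fold dose contrast (0.03/0.015 under the dose-linear PK described in the Introduction). That would need a half-life shorter than 30 minutes with the full 30-minute spread, and the protocol supplies no such figure.

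The consequence is limited to a descriptive secondary endpoint, with no hypothesis test. It is still worth correcting, because the timing of the draws has to be right when the blood is taken.

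**What to change.** 1. Reconcile the three apheresis-start statements (Synopsis, Section 6.3, Section 10.2.2), and say whether each counts from the start or the end of the infusion. This comes first: the Synopsis and Section 10.2.2 give only upper limits and Section 6.3 sets no clear minimum, so there is at present no earliest start to fit draws before.
2. In Table 8, footnote b and Section 10.1, define the same two post-dose draws as fixed times after the end of the MGTA-145 infusion that fit before the reconciled apheresis start. Keep the conditional third draw.
3. Require actual infusion and draw times to be recorded.
4. In the Synopsis and Section 12.4.3, summarize and plot means by time after end of infusion. Use actual times for individual profiles and exposure estimates.

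The cost is wording in these sections and matching text in the Laboratory Manual. No samples, visits or subjects are added.

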## 6.2. Study Duration

### 6.2.1. Duration of Treatment Part A:

Screening Period: up to 30 days

Dosing and Follow-up Period: approximately 30 days

### 6.2.2. Duration of Treatment Part B:

Screening Period: up to 30 days

Dosing and Follow-up Period: approximately 30 days

## 6.3. Methodology

Approximately 10 to 14 patients with SCD are planned to be enrolled in this 2-part study. Part A evaluates single-day mobilization and apheresis in 2 sequential patient cohorts, then Part B evaluates two-day mobilization and apheresis in a single patient cohort, following administration of single and 2 consecutive-day doses of MGTA-145 and plerixafor, respectively.

**Part A and Cohort Review Committee assessment:** Part A has a planned enrollment of approximately 7 to 11 evaluable subjects. The first cohort of 4 subjects is to receive a single

0.24 mg/kg SC dose of plerixafor followed 2 hours later by a single 0.03 mg/kg IV dose of MGTA-145. Apheresis is planned to commence within approximately 30 to 45 minutes of dosing. For this initial cohort, only one subject will be dosed and apheresed on a single-day, and each subject will complete the 1-week follow-up visit before a subsequent subject can be dosed.

After the first cohort has completed the 1-week follow-up visit, an independent Data Monitoring Committee (DMC), comprising 3 members with medical expertise in the conduct of stem cell transplantation in patients with SCD as well as the conduct of clinical trials in general, will evaluate the safety, PK, and mobilization kinetics of MGTA-145 before the second cohort may be enrolled. The DMC may recommend enrolling an additional 3 subjects at the 0.03 mg/kg MGTA-145 dose or an additional 7 subjects at a reduced dose of 0.015 mg/kg MGTA-145 or an alternative but lower dosing regimen for this cohort. The MGTA-145 dose will not be escalated during either Parts A or B.

After the second cohort has completed the 1-week follow-up visit, the DMC will likewise evaluate the safety, PK, and mobilization kinetics of MGTA-145 before subjects may be enrolled into Part B. Criteria for the DMC recommendations regarding cohort progression and dosing regimen will be defined in the DMC Charter.

**Part B:** Part B has a planned enrollment of approximately 3 evaluable subjects. Subjects will receive single doses of MGTA-145 and plerixafor on 2 consecutive days, followed by apheresis on each dosing day. The plerixafor and MGTA-145 doses on each of the 2 consecutive days will be identical to that of the second Part A cohort, unless otherwise recommended by the DMC.

All subjects in Parts A and B will be observed at the investigational site from Day -1 until at least one day after the last apheresis and attend a 1-week (7 to 10 days) follow-up visit after the last MGTA-145 infusion. All subjects will attend an EOS phone visit 30 days after the last MGTA-145 infusion.

For both Parts A and B, peripheral CD34+ cell counts will be performed pre- and post-dosing with plerixafor and post-dosing with MGTA-145, up to 5 minutes prior to apheresis ([Table 8](#)).

Hematopoietic stem cells obtained by apheresis (HPC-A) will be processed according to standardized clinical cell therapy laboratory procedures. Peripheral blood and HPC-A will be stored for testing (e.g., exploratory PD evaluation, cell characterization, and process characterization) and by the investigational sites for potential future transplantation.

## 6.4. Number of Subjects

Approximately 10 to 14 evaluable subjects with SCD are planned to be enrolled in this two-part study.

- **Part A** has a planned enrollment of approximately 7 to 11 evaluable subjects.
- **Part B** has a planned enrollment of approximately 3 evaluable subjects.

## 6.5. Treatment Assignment

This is an open-label study, in which all subjects will receive MGTA-145 and plerixafor as study drug.

All study subjects who are consented (including screen failures) will be assigned a subject identification number. The unique subject identification number will consist of 6 digits (xxxxxx).

The first 3 digits of the number will represent the study site and the second 3 digits will represent the subject at that study site. Any subject identification number that is assigned will not be reused even if a subject does not receive study drug.

## 6.6. Stopping Rules

### 6.6.1. Scheduled Stopping Rule Assessments

For the purposes of this study, a vaso-occlusive event (VOE, aka: vaso-occlusive crisis, sickle cell pain crisis) is defined as pain and/or injury as a result of ischemia due to vascular obstruction by sickled RBCs. Clinical manifestations of VOEs may include episodes of acute pain and/or evidence of organ involvement presenting as priapism, acute chest syndrome, splenic sequestration, hepatic sequestration, cerebrovascular ischemic event, or dactylitis.

Patients with SCD are known to commonly experience VOEs during and immediately following mobilization and apheresis, with approximately 30% of plerixafor-mobilized patients reported to have experienced a  $\geq$ Grade 3 VOE during and after apheresis, and approximately 20% of patients reported to have experienced serious vaso-occlusive pain within 2 days post-procedure. The stopping rules described below have therefore been designed to be triggered if the frequency of Grade 3 VOEs occurring within approximately one week (1-week follow-up visit, occurring 7 to 10 days) after MGTA-145 dosing exceeds that which would be expected using plerixafor alone, to be evaluated at each scheduled DMC assessment. Pain occurring during the infusion or immediately after infusion and resolving within 1 hour of infusion will not be considered a VOE and will not count toward the stopping rule. Furthermore, as described below in Section 6.6.1.3. (Unscheduled Stopping Rule Assessment), the occurrence of a  $\geq$ Grade 4 VOE in any subject occurring within approximately one week (1-week follow-up visit, occurring 7 to 10 days) after MGTA-145 dosing will be considered a stopping rule.

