### 6.6.1.2. Scheduled Part A, Second Cohort DMC Stopping Rule Assessment:

Based on the probability data presented in [Table 10](#) below, the likelihood of a Grade 3 VOE occurring in more than 3 of 7 subjects completing Part A within approximately one week would be 12.60%, assuming that the true incidence using plerixafor alone is 30%. Therefore, if more than 3 of 7 patients completing Part A at a specific dosing regimen report a Grade 3 VOE within approximately one week (up until the 1-week follow-up visit), the study will not progress to Part B dosing unless the DMC determines that it is safe to do so.

**Table 10: Probabilities of Grade 3 VOEs Occurring in Given Numbers of Study Subjects Undergoing Apheresis in the Second Patient Cohort of Part A Within Approximately One Week, if Mobilized with Plerixafor Alone**

Probability of $\geq$ Grade 3 VOE	Probability if True=20%	Probability if True=30%	Probability if True=40%
$\geq 1/7$	79.03%	91.76%	97.20%
$\geq 2/7$	42.33%	67.06%	84.14%
$\geq 3/7$	14.80%	35.29%	58.01%
$\geq 4/7$	3.33%	12.60%	28.98%
$>5/7$	0.47%	2.88%	9.63%
$>6/7$	0.04%	0.38%	1.88%
7	0.01%	0.02%	0.16%

Furthermore, the DMC may determine that the study should not proceed to the subsequent cohort at the current dosing regimen, based on the entirety of data available, regardless of whether a cohort stopping rule has been met.

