### 6.6.1.3. Unscheduled Stopping Rule Assessment

In addition to the cohort stopping rules outlined above, if within approximately one week (up until the 1-week follow-up visit) after MGTA-145 dosing, any subject develops a Grade  $\geq 4$  VOE, or a Grade  $\geq 3$  drug-related TEAE (based on the National Cancer Institute (NCI) Common Terminology Criteria for Adverse Events (CTCAE) version 5.0) other than VOE, dosing of the current cohort will not be continued until the DMC assesses whether dosing may continue and whether dosing modifications are needed. In addition to VOEs, Grade 3 AEs known to be associated with plerixafor (i.e., nausea, vomiting, diarrhea, headache [as per plerixafor label]) or MGTA-145 (i.e., musculoskeletal pain that is less than 1 hour in duration from the time pain is first reported) will not count toward this stopping rule.

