## 11. ASSESSMENT OF SAFETY

Subject safety will be assessed based on monitoring of AEs, vital signs, physical examinations, clinical laboratory evaluations, and development of anti-drug antibodies. Adverse events will be graded using the NCI CTCAE version 5.0.

Vaso-occlusive events are known to be associated with plerixafor use in patients with SCD undergoing mobilization and apheresis, reaching Grade 3 or higher severity in approximately 30% of patients. During each planned post-cohort assessment, the DMC is to evaluate and recommend whether to proceed to the subsequent cohort at the current dosing regimen based on evaluation of safety, PK, and mobilization kinetics. At each assessment, the number and proportion of patients reporting VOEs within approximately one week (1-week follow-up visit, occurring 7 to 10 days) after MGTA-145 dosing will be determined, and the DMC will determine whether a stopping rule has been met (Section 6.6), in which case no further dosing at that dosing regimen will take place unless the DMC determines that it is safe to do so. Pain occurring during the infusion or immediately after infusion and resolving within 1 hour of infusion will not be considered VOE and will not count toward the stopping rule.

In Part B, if a subject has a VOE following the first MGTA-145 infusion, proceeding to the second infusion will be at the Investigator's discretion.

As described below in Section 6.6, the occurrence of a Grade  $\geq 4$  VOE in any subject within approximately one week (1-week follow-up visit, occurring 7 to 10 days) after MGTA-145 dosing will be considered a stopping rule.

Excluding VOE, if any subject develops a Grade 3 or higher drug-related TEAE, based on the NCI CTCAE version 5.0, dosing of the current cohort will not be continued until the DMC assesses whether dosing may continue and whether dosing modifications are needed. In addition to VOEs, Grade 3 AEs known to be associated with plerixafor (i.e., nausea, vomiting, diarrhea, headache [as per plerixafor label]) or MGTA-145 (i.e., bone pain that is less than 1 hour in duration from the time the bone pain is first reported) will not count toward this stopping rule.

Pre-medications will be at the discretion of the Principal Investigator according to institutional or center standard for apheresis collection. All subjects will have adequate hydration before and during the apheresis procedure.

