### **13.5. Monitoring Committees**

A DMC, comprising 3 physicians with medical expertise in stem cell transplantation for patients with SCD, will evaluate the safety, PK, and mobilization kinetics of MGTA-145 after each of the 2 patient cohorts completes Part A of the study, and in the event that a stopping rule has been met, to assess whether dosing may continue and whether dosing modifications are needed.

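### Once Part A cohort 2 has started, no count of Grade 3 VOEs pauses dosing before the cohort is complete, and in Part B no count calls the DMC

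*Protocol*

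**What the plan says.** Protocol Section 6.6.1 sets the Grade 3 VOE rules to act when the observed frequency "exceeds that which would be expected using plerixafor alone, to be evaluated at each scheduled DMC assessment". Two assessments are scheduled.

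- **After cohort 1 (Section 6.6.1.1):** more than 2 of 4 subjects with a Grade 3 VOE stops further dosing unless the DMC clears it.
- **After cohort 2 (Section 6.6.1.2):** if more than 3 of 7 subjects completing Part A at one regimen are affected, "the study will not progress to Part B dosing unless the DMC determines that it is safe to do so". Section 11 words the consequence of a met rule more widely: "in which case no further dosing at that dosing regimen will take place unless the DMC determines that it is safe to do so".

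Section 6.6.1.3 adds an unscheduled pause for a Grade 4 or higher VOE. It also pauses for a Grade 3 or higher drug-related event "other than VOE, dosing of the current cohort will not be continued until the DMC assesses whether dosing may continue". Its list of events that do not count begins "In addition to VOEs, Grade 3 AEs known to be associated with plerixafor", so a Grade 3 VOE does not count.

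For Part B, Section 11 says that "if a subject has a VOE following the first MGTA-145 infusion, proceeding to the second infusion" is left to the investigator. Section 13.5 has the DMC review data "after each of the 2 patient cohorts completes Part A of the study, and in the event that a stopping rule has been met". The stagger in Section 6.3 is limited to the first cohort: "For this initial cohort, only one subject will be dosed and apheresed on a single-day", with each subject completing the 1-week visit before the next is dosed.

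**The concern.** Read together, these sections leave two stretches of the trial without a Grade 3 VOE trigger.

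The first is inside cohort 2. The threshold is read when the cohort has completed. A fourth Grade 3 VOE at a regimen while subjects are still to be dosed therefore pauses nothing.

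The second is Part B. It has no Grade 3 count and no scheduled DMC review. The DMC otherwise meets when a stopping rule is met, and a Grade 3 VOE meets none. A third subject can be dosed after both earlier subjects had a Grade 3 VOE, with no rule calling the DMC.

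Part B matters more. The Introduction calls vaso-occlusive crisis a risk with each mobilization and apheresis procedure, and Part B doubles the procedures. The only earlier two-day MGTA-145 dosing in the protocol is in 8 healthy volunteers (Phase 1 Part C), who cannot inform VOE risk. Under Section 12.1, a Part B subject whose second dose is withheld is not evaluable, and Section 12.5 allows extra subjects to reach 3 evaluable. Withheld second doses could therefore lead to more subjects being dosed, still without a trigger.

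**Working it through.** **Inputs.** The reference rate is 30%, with 20% and 40% alongside (Tables 9 and 10). The thresholds are 3 or more of 4 and 4 or more of 7. Part B has about 3 subjects. Cohort 2 has 3 more subjects at 0.03 mg/kg, or 7 new subjects at 0.015 mg/kg or another lower regimen. Subjects are taken as independent with a common rate p.

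**The protocol's own figures.** Exact binomial tails at p = 0.3:
- P(X ≥ 3 of 4) = 4(0.3³)(0.7) + 0.3⁴ = 0.0756 + 0.0081 = 8.37%
- P(X ≥ 4 of 7) = 12.60%

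Both agree with the protocol.

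**Part B.** No rule is met at any count. The chance that all 3 have a Grade 3 VOE is p³ = 0.8%, 2.7% and 6.4% at 20%, 30% and 40%. The chance that the first two are both affected, so that a pause could still protect the third, is p² = 4%, 9% and 16%.

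**Cohort 2 with 7 new subjects.** Suppose each outcome is known before the next dose. The fourth event comes before the last subject when at least 4 of the first 6 are affected:
- p = 0.3: 15(0.3⁴)(0.7²) + 6(0.3⁵)(0.7) + 0.3⁶ = 0.0595 + 0.0102 + 0.0007 = 7.0%
- p = 0.4: 15(0.4⁴)(0.6²) + 6(0.4⁵)(0.6) + 0.4⁶ = 0.1382 + 0.0369 + 0.0041 = 17.9%

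Expected subjects spared = 3·P(fourth event at subject 4) + 2·P(at 5) + 1·P(at 6):
- p = 0.3: 3(0.0081) + 2(0.02268) + 0.03969 = 0.11
- p = 0.4: 3(0.0256) + 2(0.06144) + 0.09216 = 0.29

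**Cohort 2 with 3 subjects added to cohort 1.** With the cohort 1 rule not met, the fourth event precedes the seventh subject only if cohort 1 had exactly 2 events and the next two subjects are both affected. The joint probability is P(X₄ = 2)·p²:
- p = 0.3: 0.2646 × 0.09 = 2.4%
- p = 0.4: 0.3456 × 0.16 = 5.5%

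Given that cohort 1 passed, these become 0.0238/0.9163 = 2.6% and 0.0553/0.8208 = 6.7%. At most one subject is spared.

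**Effect of reading the count early.** A count that reaches 4 cannot fall back, so reading it at the fourth event leaves the 12.60% for 7 new subjects unchanged. This needs the denominator to stay at 7. If replacements brought the number to 8, P(X ≥ 4 of 8) at 30% would be 19.4%.

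**The case against.** Part B is small and follows a DMC review. The DMC sets its dose, and escalation is barred. A Grade 4 or higher VOE still pauses dosing, as does a qualifying Grade 3 or higher drug-related event other than a VOE. Subjects stay on site until at least one day after the last apheresis, SAEs are reported within 24 hours, and the sponsor may stop for unacceptable risk. The DMC Charter, not shown, is to define criteria for cohort progression and dosing regimen. A rule on two subjects is also blunt: it would catch an assumed doubled rate of 60% only 0.6² = 36% of the time.

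These protections are real and keep the point from being a serious one. None of those in the protocol obliges a DMC review for repeated Grade 3 VOEs. The sponsor's right is discretionary, and SAE reports go to the safety vendor with no stated step to the DMC. The charter may contain a trigger, but the protocol's own rules do not. The objection to the cohort 2 part largely stands: at 30% the gain is 0.11 subjects.

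A reader might infer more than the text supports:
- **That no Grade 3 count stops dosing in Part A until cohort 2 is complete.** Section 6.6.1.1 does so after cohort 1.
- **That Section 6.6 contradicts itself.** Section 6.6.1 confines its count rules to scheduled assessments, so this is missing coverage.
- **That two-day treatment is untried in sickle cell patients.** The Introduction describes multi-day plerixafor with apheresis there. Only two-day MGTA-145 is new.
- **That 30% applies to each day.** This would give 1 − 0.7² = 51% over two days and 0.51² = 26% for both of the first two subjects. The protocol reports the 30% per patient, so the per-day reading is an assumption.

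**Conclusion.** The gap is real but limited. After cohort 2 starts, no Grade 3 VOE count pauses dosing until the cohort is complete. In Part B no count, not even 3 of 3, leads to DMC review. Part B is the part worth acting on, because it is the least-tested regimen and has the weakest Grade 3 oversight. A pause after two of two would occur with probability 4%, 9% or 16% at 20%, 30% or 40%, and could spare at most one planned subject. The cohort 2 part is minor: the fourth event precedes the last of 7 new subjects in 7.0% (30%) or 17.9% (40%) of cohorts, and earlier reading gains nothing if dosing is concurrent.

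The figures rest on independent subjects, a common rate within the protocol's 20% to 40% range and, for cohort 2, outcomes known before each next dose. Any rate above 40% is an assumption.

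**What to change.** **Main change (Sections 6.6 and 13.5).** In Part B, dose one subject at a time through the 1-week visit, as in cohort 1. If the first 2 subjects both report a Grade 3 or higher VOE, dose no further subject until the DMC has reviewed the data. Wording it as no further subject also covers any replacement.

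**Minor change (Section 6.6.1.2, listed in 13.5).** Keep the threshold of more than 3 among the first 7 evaluable subjects at a regimen. Apply it as soon as the fourth is reported, pausing further dosing at that regimen until DMC review. State the denominator of 7, so that replacements do not raise the trigger chance.

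**Cost.** A protocol amendment and matching charter text; the DMC already exists. Part B gains two waits of about 8 to 11 days, from the follow-up window in Table 7. If the true Part B rate is no worse than the 30% reference, the chance of an unneeded pause is 9%. The cohort 2 change adds no triggers for 7 new subjects and only brings the existing one forward.
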